**Study Title: Personalized experiences to inform improved communication for minorities with Life Limiting Illness**

**I. Specific Aims**

Comprehensive palliative care improves quality of life (QoL) for patients with life-limiting illness (LLI). There is a growing population of racial and ethnic minority patients with LLI in the United States who are underserved by health care in many ways, including in both access to and quality of palliative care. Specific disparities have been reported in palliative care for minority patients, in part because of gaps in knowledge around patient-centered psychological, social, and spiritual palliative care interventions. Studies also show differences by race and ethnicity in patient receipt of and preferences for life-sustaining technologies in the context of LLI. Minority patients with LLI report a desire to discuss their care preferences with health care providers, yet do so at a much lower rate than white patients. Even more concerning, minority patients with LLI often do not receive treatment consistent with their wishes. Poor patient-provider communication contributes to the provision of aggressive care for many minority patients who do not want it.

Patient-centered palliative care practice must be informed by the perspectives of patients living with LLI. An increased understanding of psychological, social, and spiritual needs from the patient's perspective will help providers develop tailored palliative care interventions centered in patient's cultural values and beliefs.

Storytelling is an effective way to communicate cultural values and beliefs. In the health care setting, the electronic health record (EHR) is one of the primary modes of communicating information about patients to all providers. Incorporating a patient's story into the EHR is an opportunity to more fully incorporate the patient's cultural values and beliefs into their care. Thus, integrating minority patients' stories into the EHR has the potential to improve patient-provider communication around minority patients' values and beliefs. Yet there is a lack of research about how to effectively integrate patient stories into the EHR. This proposal focuses on investigating an innovative way to integrate patient values and beliefs into the EHR through a storytelling intervention.

My *long-term goal* is to improve palliative care for minority patients with LLI by facilitating communication between patients and their health care providers. The *objectives of this grant and proposed studies* are to assess the feasibility and efficacy of a storytelling intervention designed to improve communication of values between patient and provider. The *central hypothesis* of this proposal is that implementing a patient-centered storytelling intervention with minority patients will result in improved patient-provider communication about these patients' care preferences, based on the cultural values and beliefs that underlie those preferences. The assembled mentoring team is well prepared to support the proposed research with a unique combination of skills and experience in palliative care, storytelling, mixed methods, and informatics.

**K99 Phase: Storytelling Intervention Design (Define and Refine)**

**Specific Aim 1:** Identify barriers and facilitators for the storytelling intervention from the perspectives of the key stakeholders—minority patients with LLI and acute-care bedside nurses—through patient and nurse exit interviews; and field analysis of EHR interface use and end-user surveys of the nurses.

**Specific Aim 2:** Conduct usability testing, applying a user-task-system-environment evaluation process to determine essential requirements for integration and use of the patient-centered story into the EHR, from the perspective of an important end user: the acute-care bedside nurse.

**Impact**

The proposed study aligns clearly with NINR's strategic focus on palliative care science, addressing health disparities, and evaluating patient-centered interventions to optimize QoL. This proposal builds on my prior research experience with narrative analysis methodology. It is *innovative* in that incorporating meaningful use of the EHR is a new approach to improving patient-provider communication. The *expected outcome of the K99 phase* will be the refinement of a storytelling intervention. The *expected outcome of the R00 phase* will be

completion of a proof-of-concept of the storytelling intervention. This proposal will build a program of patient-centered research with racial and ethnic minority populations and provide the foundation for future R01 applications for developing, testing, and tailoring patient-centered communication interventions.

## II. Background and Significance

**Palliative Care Decreases Suffering in Patients with Life-Limiting Illness.** Health care advances have extended the lifespan and cured many diseases. Advanced health care technologies can also encourage aggressive, life-extending, yet sometimes non-beneficial treatments for patients with life-limiting illness (LLI), at the expense of psychosocial and spiritual support. Depression, anxiety, and physical/emotional suffering have been reported by patients receiving life-extending treatments. Decreased depression and improved QoL has been reported when patients receive palliative care early in the course of their illness. As the population of minorities with LLI increases, there is increasing need for patient-centered palliative care interventions that are consistent with patients' cultural values and beliefs. Research that improves communication between providers and patients, decreases suffering, and improves QoL for this population is an urgent need.

**Importance of Addressing Racial/Ethnic Disparities in Palliative Care.** Disparities between white and racial and ethnic minority patients have been reported in both access to and quality of palliative care services. Culture influences health behaviors and the meaning of illness. Minority patients with LLI have experienced insufficient symptom control, difficult interactions with their health care providers, and lack of psychosocial and spiritual support. Patient-centered communication interventions can provide better knowledge about the psychological, social, and spiritual experiences of racial and ethnic minority populations with LLI. For instance, gathering stories about a patient's illness experiences can give health care providers a view into the patient's cultural values, attitudes, beliefs, and/or preferences of care. Health care provided through a culturally sensitive, patient-centered framework may improve quality of communication between providers and patients. Improved communication leads to care that is more consistent with patients' cultural values and beliefs. *While research examining cross-cultural psychological, social, and spiritual experiences of patients with LLI is increasing, it remains limited in scope, quantity, and settings.*

### A Narrative Communication Intervention Can Improve Outcomes for Minority Patients with LLI.

Palliative care providers are well-positioned to support minority patients' psychosocial and spiritual well-being through narrative communication interventions. Story theory is based on the foundation of "meaning making"34,pg.205 and can be applied to communication between nurse and patient. The theoretical basis of story theory is built on three concepts: intentional dialogue, creating ease, and connecting with self-in-relation. According to story theory, when a nurse knows more of the patient's illness story, both direct and indirect effects occur. These effects provide opportunities for the type of culturally congruent care that leads to improved QoL and can lessen suffering for minority populations with LLI. Through the method and practice of listening to minority patients' stories, cultural aspects of psychological, social, and spiritual dimensions of care for minorities with LLI can be discovered. A storytelling intervention that elicits patients' psychological, social, and spiritual experiences can contribute to culturally sensitive, patient-centered care that

recognizes and brings attention to differences in patient values, preferences, and expressed needs. *Addressing gaps in knowledge around the cultural values and beliefs of minority patients can lead to reduced suffering among minority patients with LLI.*

**Theoretical Framework.** In this proposal's conceptual framework (see Figure 2), the palliative care approach integrates cultural beliefs and values of physiological, psychological, social, and spiritual healing. Healing and suffering are on a continuum centered around the patient's social, spiritual, psychological, and physical experiences of LLI.

## Innovation

[name]\_COMIRB:17-885\_V1\_101817

Adapted from: NCP Clinical Practice Guidelines for Quality Palliative Care, NQF for Palliative and Hospice Care Quality and Healing Connections: QoL continuum by Mount, Boston & Cohen

**Storytelling Can Be a Culturally Sensitive Patient-Centered Communication Intervention.** A storytelling intervention can draw together the complexities of LLI experiences and the varied cultural meanings of illness by collecting, analyzing, and sharing illness stories of minority patients living with LLI with the healthcare team. Storytelling interventions have been shown to improve QoL and to decrease suffering. Patient participation in storytelling interventions has been linked to reduced levels of pain, stress, anxiety, and fatigue, and to improved psychosocial and QoL outcome measures. Some research has integrated narrative interventions such as life review on DVD and digital storytelling uploaded to YouTube to be shared with families and found positive outcomes. However, little is known about storytelling specifically for minority patients with LLI and whether storytelling could improve communication and thereby improve patient and family outcomes. Research is needed to understand if and how storytelling interventions can improve patient-provider communication, which may be one of the mechanisms for improving psychosocial outcomes and QoL for patients with LLI.

### **III. Preliminary Data**

**Preliminary study.** My dissertation research used narrative analysis and collected African American elder illness experiences in the form of co-created stories. Through this process, the next logical step was to begin testing a storytelling intervention. In the proposed studies, I will investigate the potential effects on patient-centered communication intervention of using written meta-stories within the EHR. This proposal is to define and refine a storytelling intervention and test its mechanisms, feasibility, and effects. This research will enroll only patients from racial/ethnic minority groups, because expert input from minority patients improves the likelihood of developing a culturally sensitive intervention.

**Storytelling Has Never Before Been Included in the Electronic Health Record (EHR).** Integrating patient stories into the EHR could benefit patients and providers who interact in increasingly technology-rich health care environments. Since the EHR is one of the primary modes of communicating health care information about the patient, the integration of minority patients' stories into the EHR has the potential to improve patient-provider communication around patient-centered values and beliefs. Yet, there is a lack of research about how to integrate patients' stories into the EHR in a meaningful, efficient, and effective way.

**Relevance of Research to Palliative Care Science.** A program of research around patient-centered communication interventions can contribute to enhancing QoL among racial and ethnic populations of patients with LLI. At this time, to decrease the complexity of the intervention, only written stories will be tested; future studies could incorporate video or audio stories as well. These and future studies within this theoretical approach will provide input into a much-needed area of study of patient-centered communication interventions with potential to promote psychological, social, and spiritual healing for minority populations with LLI. The proposed program of research has the potential to improve communication between providers and patients, and aligns with NINR's strategic focus on resolving health disparities and promoting palliative care practices that improve QoL for patients with LLI.

**Relevance of Research to My Career Goals.** My research career goals are guided by the Obesity-Related Behavioral Intervention Trials (ORBIT) model for the development of programs of research in behavioral intervention (see Figure 1 in Candidate Goals and Objectives section). Using Riessman's narrative methods for human sciences in a population of aging African American elders, for my dissertation I completed an exploratory descriptive design using a narrative analysis methodology. Following my dissertation, I developed a significant research question: How can narrative interventions be used to improve communication among patients with serious illness and their providers? My in-depth study of narrative methodologies, coupled with my years of palliative care nursing practice, helped me recognize the utility of narrative as an intervention to improve psychological, social, and spiritual suffering across myriad illness states and across many cultures. The phase of this training plan builds on my completed dissertation research and continues Phase I of the ORBIT model in defining and refining a storytelling intervention.

### **IV. Research Methods**

#### **Approach: Define/Refine a Storytelling Intervention (ORBIT Model Phase I)**

**A. Design and Outcomes.** For this study, I will use an observational design to define and refine the storytelling intervention, seeking input from the key stakeholders: patients (minority patients with LLI) and providers (acute-care bedside nurses). Outcomes from this study will provide the in-depth understanding necessary to refine a culturally sensitive patient-centered storytelling intervention.

## B. Description of Populations to be Enrolled.

**Setting/sample.** This study will take place at University of Colorado hospital. The participants will be minority patients with LLI and their bedside nurses. Purposeful sampling strategies will be used to recruit participants. The plan is to obtain consent from 24 patient participants equally divided (8 patients each) among three diagnostic groups: cancer, COPD, and heart failure. Data will also be collected from 12 nurse participants who provided care to the participating patients. The small sample size was chosen to be consistent with both qualitative data analysis techniques and usability data analysis techniques.

**Patient eligibility criteria.** Patients will be 18 years of age or older; able to read English; capable of giving informed consent; self-identifying as part of a racial or ethnic minority; and diagnosed with at least one LLI. The operational definition of LLI eligible for this study includes the following diagnoses: (1) metastatic solid cancer or inoperable lung cancer; (2) COPD with FEV1 values < 35% predicted or oxygen dependence; (3) New York Heart Association Class III or IV heart failure (CHF). The disease criteria were chosen to identify groups of patients with a median survival of about 2 years. These diagnoses represent 3 of the major causes of death related to LLI in the United States. Due to the nature of the qualitative design and geographical location census data, a broad group of racial/ethnic groups will be eligible to participate to allow for maximum variation sampling to collect acceptability data from a variety of groups.

[figure not shown]
**Nurse eligibility criteria.** All participating nurses will be 18 years of age or older and able to read English, and will confirm verbally that they were involved in the care of a patient who is participating in the storytelling intervention. Bedside nurses were specifically chosen as provider participants due to amount of time they interact with inpatients and the frequency with which they interface with the EHR compared to other team members. In future R01 studies of this intervention, other members of the patient's care team will be added.

## C. Research Methods

**Patient recruitment.** I will attend University of Colorado inpatient nurse staff meetings to introduce the study, identify potential units with potential patient participants and post recruitment flyers on units. Once these units are identified, I will attend nursing rounds to identify potential patients with the assistance of the nursing care team. If a potential patient is identified by a nursing care team member, that member will provide a flyer to potential participant and obtain verbal consent. Nursing care team members will notify me of patients who provide verbal consent via secure, encrypted e-mail. I will then arrange a convenient time to meet with each patient to review the study protocols, complete screening and obtain informed consent. The consent process and the storytelling intervention interview will occur in the patient's private inpatient room. Based on my dissertation research, I anticipate that this process will take 60–90 minutes of the patient's time. For the burden of time, each patient who completes the storytelling intervention interview will receive \$50 in appreciation, plus an additional \$50 at the time of the exit interview. If the patient is discharged from the hospital, the follow-up exit interview will be collected via telephone.

**Nurse recruitment.** After a patient story is added to the EHR (see Data Collection/Analysis), I will collect from the EHR the names of the nurses who cared for the patient. These nurses will be approached for consent to participate in the study, with the goal of 12 participating nurses. For the user-centered testing, an additional 6 nurses will be recruited, for a total of 18 nurse participants. Nurses will be contacted via e-mail with a recruitment flyer. After receiving verbal consent for participation via e-mail, a convenient in-person time will be coordinated for data collection for the exit interviews. Weekly follow-up e-mails will be sent if there are difficulties recruiting the 24 nurses for data collection or the 6 nurses for user-centered testing. For the burden of time, each nurse completing the study will receive \$100 in appreciation.

**Storytelling intervention.** As principal investigator (PI), I will conduct a storytelling intervention interview with each of the patient participants. During the interview, I will prompt the participant to share their story using probing questions such as these: tell me about your illness, tell me how your illness has affected your emotions, your relationships, your spirituality. This storytelling intervention has been field tested during my prior dissertation research (see Appendix B. Storytelling Interview Guide). I will read the prompts, concurrently take field notes of the participant's

responses, and audio-record the interview. The de-identified audio recording will be delivered via an encrypted e-mail to the transcriptionist. After the interview has been transcribed, I will review the transcripts for accuracy and create a 1- to 2-page meta-story of the participant's responses. Criteria are that the meta-story (1) is written in the first person; (2) is nonjudgmental; (3) captures the participant's voice; (4) accurately reflects the content of the interview; and (5) is nondiagnostic (not labeling). I will complete and return each meta-story to the patient participant within 48 hours. The participant and I will review the meta-story on my password-protected computer, and the participant will be encouraged to make any desired changes, facilitating co-creation of the meta-story. Once the meta-story has been approved by the participant, I will upload it to the EHR (see Appendix C. Exemplar of Meta-Story). Automated alerts, built within the EHR, will be sent to the participant's EHR-assigned nurse once the meta-story has been uploaded. To decrease complexity of the study design at the define-and-refine phase, only acute-care bedside nurses will be recruited to participate, thus acute care bedside nurses are the only providers who will receive the alert and participate in the usability testing. This workflow is depicted in Figure 3.

#### **D. Data Collection/Analysis.**

**Specific Aim 1: Barriers and facilitators.** Two weeks after the meta-story is added to the EHR, both patient and nurse will be contacted for exit interviews to collect information about barriers and facilitators of the intervention (see Appendix D. Exit Interview Guide). The transcribed exit interviews will be entered into ATLAS.ti (a qualitative data management/analysis program). An interpretive approach will inform the understanding of the patients' and nurses' perspectives related to barriers and facilitators. Open coding, which allows codes to form patterns as they emerge from the transcripts, will be used for the thematic analysis. An inductive approach to coding, through the use of the participant's actual words, will be used for up to 3 transcripts. Once the initial codes are chosen, the transcripts will be read again through an iterative process defined as "a movement back and forth through" data coding for creating thematic analyses.54(p86) As PI, I will complete the preliminary coding for each transcript. Then the research team, which includes my primary mentor, [name], and my co-mentor, [name], will review my preliminary codes. Once the first 3 transcripts are coded, the research team will analyze the preliminary codes across the remainder of the transcripts. Throughout the entire analytical process, the codes will be refined and defined more clearly. At each of the monthly research team meetings, codes can be expanded or similar codes collapsed into larger codes as part of the iterative process for arriving at the final themes. To ensure the rigor of the data analysis, Sandelowski's criteria for trustworthiness (credibility, applicability, consistency, and neutrality) will be used.

**Specific Aim 2: Usability testing.** Usability is defined as the relationship between humans and computers. Usability testing focuses on evaluating process measures based on four major components: user (nurse), task (utilization of meta-story by nurse), system (meta-story in EHR), and environment (inpatient nurse's station). The user-task-system-environment framework of process measures will be incorporated into the usability testing to determine barriers and facilitators from the perspective of the bedside nurse and to help determine the essential requirements for integrating the patient-centered storytelling intervention into the EHR by evaluating information flow, use of information, and system functionality. The process measures collected to determine usability will include the following: field observations of the end user (the nurse); chart review/log analysis of the nurse's use of the patient's story; time/cost analysis of the collection of the story, which includes transcribing the story, writing and co-creating the meta-story, uploading the final meta-story into the EHR, and exit interviews for both patient and nurse participants. In addition, time log analyses will be completed. These analyses will include recording the uses of the meta-story by all providers, not just the acute-care bedside nurse, to evaluate if other providers accessed the meta-story, how many times, and for what length of time the meta-story was accessed. These exploratory analyses will inform the design of future studies and how they can incorporate other types of providers as participants.

For user-centered testing, I will recruit 6 nurses to test the workflow processes. The participating nurses will (1) provide content expertise of the workflow processes, and (2) put the storytelling intervention through in-house usability testing to check the "strength" of the EHR features as well as the level of user-friendliness. The goal is to make using the storytelling intervention as intuitive as possible. Prior research shows that testing with 5 participants identifies 85% of usability issues. Testing will assess ease of use, relevance and appeal, efficiency, error frequency and severity, and subjective satisfaction with the presentation of the meta-story in the EHR. Following the session, the participants will be debriefed and asked to complete a questionnaire modeled after the System Usability Scale (SUS), which asks them to rank their experience and satisfaction

with specific elements (such as where the meta-story is labeled and presented in the EHR, technical difficulties, use of the material, trust in the material, and ability to navigate within the EHR).

**Expected Outcomes.** The expected outcomes of the phase will be the completed design of a patient-centered storytelling intervention. Understanding of the patterns of barriers and facilitators of the storytelling experience from the perspectives of the key stakeholders, and evaluating the usability of the EHR integration, will inform the development of the intervention.

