## **E. Potential Problems and Alternative Strategies.**

**Patient burden.** Thinking and conversing about end-of-life preferences and overall QoL may initially distress some patients and families. Some patients may decide not to participate because these issues are too difficult to deal with in the context of their illness. I have expertise from prior research experience in collecting patients' stories, and I will use strategies to conduct the conversations with a minimum of associated distress/anxiety to avoid increasing suffering. Participants' distress will be evaluated throughout the intervention, from initial audio-recording to integration of the meta-story into the EHR. A referral plan is in place for appropriate follow-up services as needed for any increased level of participant distress. If distress occurs, the participant can withdraw. To evaluate acceptability and feasibility, withdrawal data will be collected in a protocol log and discussed at research meetings; adjustments to the protocol will be completed as necessary.

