## **F. Protection of Human Subjects**

### **Risks to Human Subjects**

#### **a. Human Subjects: Involvement, Characteristics, and Design**

A purposive sample of patient-nurse dyads will be enrolled in this study. Participants in this study are minority patients with life limiting illness (cancer, COPD, or heart failure) and their health care nurses. We expect to enroll 24 minority patients with life limiting illness and 18 nurses who are directly involved in the care of the patient. The principal investigator (PI) will enroll all participants after each of them voluntarily decide to become a participant.

**Patients.** Each patient participant will engage in two audio-recorded interviews lasting approximately 60-90 minutes. For the first interview, through a narrative analysis framework, the patients will answer open-ended questions related to their illness experiences and how their illness has impacted their emotions, relationships and spirituality. (See Appendix A-Storytelling Interview Guide). For the second interview, the patient will answer exit interview questions to capture their experience of the storytelling intervention. For the patient interviews, the location will include their private inpatient room or private conference room in the facility. If the patient is discharged prior to the second exit interview, the exit interview may take place over the telephone. (See Appendix B-Exit Interview Guide).

**Nurses.** The nurses will be interviewed once. This interview will capture exit interview data related to the storytelling intervention. The participant and nurse will be interviewed at separate times. For the nurse interview, the PI will coordinate a convenient and private place to conduct the interview which might include nurse's office or private conference in the facility. (See Appendix B- Exit Interview Guide). For the usability testing, the PI will coordinate a convenient time between at the nurse's convenience to conduct the user-task-system-environment evaluations.

The following characteristics will determine the eligibility for patient participants and nurse participants. Eligibility criteria will first be determined by the patient participant, who must be:

- (1) Over age age 18
- (2) Able to speak English
- (3) Be capable of giving informed consent
- (4) Self identify as being a racial/ethnic minority and
- (5) Have one of the following LLI: cancer, COPD, or heart failure.

Eligibility criteria for the nurses are that they be:

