- (1) Nurses will be at least age 18
- (2) Able to read, speak and write English
- (3) Confirm verbally that they were involved in the care of the patient who received the storytelling intervention.

Data collection activities for patient participants include completing the storytelling intervention via a 60-90 minute audio-recorded interview and completing an exit interview via a 60-90 minute audio-recorded interview. Data collection activities for the 12 nurse participants will include completing a 60-90 minute exit interview via an audio recorded interview. For the usability testing, data collection will include testing of the EHR interface with the bedside nurses and completion of a short questionnaire at the end of the hour session.

**Setting:** The participants will be recruited through the University of Colorado hospital.

b. **Sources of Materials**

Data for this proposed project will only be collected by the PI. Materials include audio-recordings of interviews, field notes, and correspondence (i.e., memos, emails) with research team members. A total of 60 audio-recorded interviews will be collected; 24 interviews for the storytelling intervention; 24 for the patient exit interviews, 12 for the nurse exit interviews. Safeguards for protecting anonymity of participants will include creating a master list of names with corresponding numbers assigned to participants at the time of the screening by the PI. Once assigned, the corresponding numbers will then be used to de-identify the remainder of participants' personal information and each participant's interview transcript. Only de-identified transcripts of interviews will be available for the remainder of the research team for analysis and interpretation processes.

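### Patient exit interviews are scheduled only after EHR upload, so enrolled patients whose story is never uploaded have no stated route into the Aim 1 barrier analysis

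*Protocol*

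**What the plan says.** Aim 1 is to identify barriers and facilitators from the perspectives of patients and nurses, "through patient and nurse exit interviews; and field analysis of EHR interface use and end-user surveys of the nurses" (K99 Phase, Specific Aim 1).

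The timing rule is in D. Data Collection/Analysis: "Two weeks after the meta-story is added to the EHR, both patient and nurse will be contacted for exit interviews". The same paragraph names the transcribed exit interviews as the material for thematic coding. Upload has its own condition, in C. Research Methods, Storytelling intervention: "Once the meta-story has been approved by the participant, I will upload it to the EHR".

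On numbers, B. Description of Populations says: "The plan is to obtain consent from 24 patient participants equally divided (8 patients each) among three diagnostic groups". Under Protection of Human Subjects, "Each patient participant will engage in two audio-recorded interviews lasting approximately 60-90 minutes". Sources of Materials adds: "A total of 60 audio-recorded interviews will be collected; 24 interviews for the storytelling intervention; 24 for the patient exit interviews", with the remaining 12 being nurse exit interviews.

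Discharge is handled by a change of mode: "If the patient is discharged from the hospital, the follow-up exit interview will be collected via telephone" (C. Research Methods, Patient recruitment). For patients who leave the study, "withdrawal data will be collected in a protocol log and discussed at research meetings" (E. Potential Problems), with the stated purpose of judging acceptability and feasibility.

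**The concern.** In a study of barriers, a patient who stops telling the story, does not want it in the record, or goes home before reviewing it is well placed to describe one. Under the timing rule as written, that patient has no exit interview date. The interview sample is then selected on having passed through the steps whose barriers are being studied.

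Because Aim 1 is inductive thematic work in a small purposive sample, the risk is less a biased percentage than a missing theme. The protocol says that these findings will inform development of the intervention (Expected Outcomes), so a barrier that acts before upload could go into the next phase unexamined.

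**Working it through.** **1. The rule and its condition.** Consent leads to the storytelling interview, transcription, a story returned within 48 hours, review and approval, upload, and an exit interview two weeks later. Every step before upload is a point of possible loss, and no section gives an exit interview date to a patient lost at any of them.

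**2. Loss is foreseen.** E. Potential Problems expects that some patients may be distressed and says they can withdraw. Potential Risks, Psychological, lets a distressed patient stop, reschedule or withdraw consent. Discharge is a further route. The telephone option covers the exit interview only, while review of the story takes place with the investigator on the investigator's computer. Further changes are made in person (Protections Against Risk, Confidentiality). No remote review is described.

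**3. What else is recorded, and whether it reaches Aim 1.**
- Withdrawal log: covers withdrawals. It does not cover a patient who stays enrolled without approving the story, and it is not said to record reasons or to enter the coding.
- Field notes on each interaction, and the inquiry into reasons for referrals for moderate or severe distress: both sit in the Data and Safety Monitoring Plan, and neither is linked to Aim 1 coding.
- Nurses for exit interview: their names are taken from the EHR after a story has been added (Nurse recruitment), so this source too depends on upload.

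**4. The protocol's own count.** 24 + 24 + 12 = 60, which reproduces the stated total. With 24 patients consented, 24 exit interviews under an upload-only rule require zero loss before upload. No replacement of lost patients is described.

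**5. Sensitivity to loss.** The protocol gives no loss rate, so d, the share lost before upload, is assumed, with losses independent between patients.

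| d (assumed) | Exit interviews, 24(1 − d) | Per group of 8, 8(1 − d) | Chance that at least one is lost, 1 − (1 − d)^24 | Consents needed for 24 exits, 24/(1 − d), rounded up |
|---|---|---|---|---|
| 5% | 22.8 | 7.6 | 71% | 26 |
| 10% | 21.6 | 7.2 | 92% | 27 |
| 20% | 19.2 | 6.4 | 99.5% | 30 |
| 30% | 16.8 | 5.6 | over 99.9% | 35 |

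The last column shows what recruitment alone could do. It restores the count of 24 but not the group that is missing.

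**The case against.** The strongest reply is that the sentence in D says when contact happens and does not bar anyone. Two interviews are planned for each patient, and the telephone provision does not mention upload. The consent section speaks of exit interviews after the intervention. The workflow figure (Figure 3) is not in the text available to me and might contain a branch for stories not uploaded. The 48-hour turnaround also keeps the window for loss short. This stands as a reason for caution about intent. It does not supply a date, or a route into the coding, for these patients.

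Three stronger readings are tempting but not supported.

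- A reader might infer that patients without an upload contribute no barrier information at all. The log, the field notes and the referral inquiry contradict that, and the log and the referral inquiry can lead to changes in the protocol.
- A reader might infer that Aim 1 hears only from patients for whom the intervention worked. Upload shows only that a text was approved and posted. Those patients can still report distress, burden or a story that nobody used, and Aim 1 also draws on nurses and EHR use.
- A reader might infer that stopping the intervention ends all data collection. Potential Risks, Psychological, lists refusing the intervention separately from complete withdrawal. Data collection ends only where data reveal increased distress, dissatisfaction or an adverse event, and involvement ends after a serious adverse event.

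Nor can a bias be computed by assuming how common a barrier is with and without upload. Aim 1 estimates no proportion, and the answer would only return the assumption.

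**Conclusion.** The concern holds in a limited form. Followed as written, the protocol draws its patient exit interviews, and so its patient barrier themes, only from patients whose story was uploaded. It also counts 24 exits from 24 consents with no allowance for loss. Information on the others is partly collected but has no stated path into Aim 1.

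The size of the effect on the findings cannot be derived from the document. The fall to about 23 to 17 exit interviews rests on an assumed 5% to 30% loss, and the chances of at least one loss rest on independence as well. The conclusion also assumes that Figure 3 does not add a branch that the text omits. This is a data-collection rule that the protocol itself fixes, so it should be corrected there.

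**What to change.** In D. Data Collection/Analysis, Specific Aim 1, offer the exit interview to every enrolled patient who has not withdrawn consent to contact: two weeks after upload or, if no story is uploaded, two weeks after the storytelling interview. Name a date also for a patient who consented but never began that interview. Make the offer voluntary, and allow a short telephone version. Code these transcripts within Aim 1 as a labelled group: story not uploaded, with the reason.

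Reconcile the offer with the statements in Potential Risks and Protections Against Risk that data collection ends, or involvement is discontinued, after distress, dissatisfaction or an adverse event. For patients covered by those statements, bring the reasons already held in the log and field notes into the Aim 1 analysis instead of seeking an interview.

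The cost is protocol and consent wording. No interviews are needed beyond the 24 already planned. Some patients will decline, so the gap will narrow rather than close, and the offer must be made without pressure.
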